5.3.2 COMPLIANCE & ADHERENCE

If a baby in the control group receives chlorhexidine skin application, this may be due either to inadvertent application of the procedure (e.g. due to error thinking the baby is in an intervention group), or due to routine use of chlorhexidine, for example for an invasive procedure. Both will be recorded on trial CRFs/worksheets. In the case of routine use for a specific purpose related to routine clinical care (for example local application prior to insertion of a vascular device), this will be recorded but not classified as a protocol deviation, whereas if a baby inadvertently receives an application designed for a baby randomised into an intervention group, then this will be recorded as a protocol deviation.

5.4 UNBLINDING / UNMASKING

NeoCHG is an open label trial and therefore there is no unblinding/unmasking.

5.5 PROTOCOL TREATMENT DISCONTINUATION

In consenting to the trial, parents/carers are consenting to trial treatment, trial follow-up and data collection. However, an individual baby may stop treatment early for any of the following reasons:

- Unacceptable toxicity or adverse event
- Intercurrent illness that prevents further treatment
- Any change in the baby's condition that justifies the discontinuation of treatment in the clinician's opinion, including neurological disturbance developing at any point during the trial
- Inadequate compliance with the protocol treatment in the judgement of the treating clinician
- Withdrawal of consent for treatment by the parent/carer

As the baby's participation in the trial is entirely voluntary, the parent/carer may choose to discontinue the baby's trial treatment at any time without penalty or loss of benefits to which they are otherwise entitled. Although the parent/carer is not required to give a reason for discontinuing their trial treatment, a reasonable effort should be made to establish this reason while fully respecting their rights.

Babies should remain in the trial for the purpose of follow-up and data analysis (unless the parent/carer withdraws their consent from all stages of the trial). If a baby is withdrawn from follow-up, refer to Section 6.5.

Data already recorded will be kept for babies who stop follow-up early.

5.6 COMPLIANCE & ADHERENCE

Adherence to allocated interventions will be recorded on CRFs/worksheets. Compliance is expected to be high because the allocated intervention is administered in hospital.

5.7 DATA COLLECTION

Baseline, treatment and follow up data including information about all antibiotics and concomitant topical medication received will be recorded on CRFs/worksheets. Other concomitant medications will not be recorded.

5.8 NON-TRIAL TREATMENT

5.8.1 MEDICATIONS PERMITTED

After entry into the trial, any concomitant medication which is required is permitted, including any antimicrobials. Topical treatments and antibiotics will be recorded on CRFs/worksheets.

5.8.2 MEDICATIONS NOT PERMITTED

As an inclusion criteria parents will be asked to agree not to apply routine emollients outside of the trial procedures. However, if they decide to do so, any such emollient use will be recorded on trial CRFs/worksheets but will not be counted as a protocol deviation as it will be done by the parent or carer, outside the control of the trial team. Babies should continue to be followed in the trial, regardless of whether the parent/carer follows the allocated regimen.

5.8.3 MEDICATIONS TO BE USED WITH CAUTION

Chlorhexidine may be required for routine care in any group, such as an invasive procedure. When used outside of the trial procedures this will be recorded in the CRF/worksheet and will not be considered as a protocol deviation if it is for routine care.

5.8.4 TREATMENT AFTER TRIAL EVENT

Treatment will be at the discretion of the responsible clinician.

5.9 CO-ENROLMENT GUIDELINES

Co-enrolment in previous or future trials is considered in Section 4.3.

6 ASSESSMENTS & FOLLOW-UP

6.1 TRIAL ASSESSMENT SCHEDULE

The trial assessment schedule is described in Table 1.

After screening, baseline data including mode of delivery, birth weight, gestational age, comorbidities, and postnatal antibiotic history will be collected. The skin will be assessed, and the baseline skin score determined.

Swabs will be taken, and temperature will be checked before each application of chlorhexidine +/emollient. After the product(s) has been applied, the body temperature should be measured after 15 minutes. A further assessment of the skin will be carried out at 30 minutes post application. Babies randomised to the control group will have swabs taken and temperature checked once on the same days as babies randomised to the alternate working day schedule.

Microbiological assessments will be performed with a nose, cervical skin fold and umbilicus (pooled) swab and a separate peri-anal swab. The timing of these swabs is described in **Table 1**, and must be taken before any application of chlorhexidine and emollient.

6.2 PROCEDURES FOR ASSESSING EFFICACY

Efficacy will be measured as change in colony forming units (CFUs) with one swab from the nose, one combined swab (cervical skin folds and umbilicus pooled) and one peri-rectal swab from randomisation (before chlorhexidine application) to day 3+/- 1 day and day 8 +/- 3 days of the trial. Swabs will be vortexed in liquid transport medium, inoculated in serial dilutions on MacConkey and blood agar, and read after 24 hours incubation. Both total bacterial load (total CFU) as well as pathogen specific CFUs will be recorded.

6.3 PROCEDURES FOR ASSESSING SAFETY

Safety will be assessed using a modified skin score which assesses the skin condition, and presence of erythema, dryness, and any other sign of skin damage (see **Appendix I**). This will be performed before each application of chlorhexidine or emollient and 30 minutes after the product(s) application. The skin score will be considered as both an absolute value and graded. Skin score assessments will be performed once every working day on all babies to provide unbiased comparisons across randomised groups. At other times, skin score assessments will be performed as required if there is clinical concern.

In addition, temperature will be measured before, and 15 minutes after application, to monitor for hypothermia. Hypothermia will be graded as follows:

- Grade 1: 35.5 36.0C
- Grade 2: 35.4 35.0C
- Grade 3: 34.0 34.9C
- Grade 4: <34.0C

Other adverse events will be reported as described in Section 7.

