ASSESSMENTS						D	AYS II	N TRIA	۹L		
					Week :	1			Wee	< 2	Final follow up
Face to face visit	Screening	Random-	Day	Day	Day	Day	Day	Day	Day	Day	Day 28
Face to face or telephone	D-1 to D1	isation D1	1	2	3	4	5	8	9	10-14	
Trial participation		1									
Eligibility	Х										
Parent/carer information sheet	Х										
Informed consent	Х										
Enrolment form and		X									
randomisation ^a											
Clinical assessments											
Baseline data collection ^b	X										
Weight	Х									Х	
Temperature ^c	Х		Х	Х	Х	Х	Х	Х	Х	Xi	
Skin Score ^d	X		Х	Х	Х	Х	Х	Х	Х	Xi	
Adverse Events	Х		Х	Х	Х	Х	Х	Х	Х	X ⁱ	
Microbiology											
Nose swab ^e			х		Xe			Xe			
Cervical skin fold & umbilical swabs (pooled) ^f			х		Хţ			Xf			
Rectal swab ^g			Х		Xg			Xg			
CHG ± emollient application ^h			Х	(X)	Х	(X)	Х	(X)	Х	Xi	
Final follow up											Xj

Additional explanatory notes for investigations

Intervention & assessment days are on working days – if a day falls on a non-working day then shift next activity to the closest working day, whatever the working pattern. Alternate working days are Monday, Wednesday, Friday; or Tuesday, Thursday, Saturday, depending on the standard working pattern in each country.

^a Enrolment form completed and data entered into the database. Randomisation completed electronically.

^b Includes collecting medical history, mode of delivery, birth weight, gestational age, co-morbidities and antibiotic history. ^c Temperature to be collected once at screening. Temperature to be collected BEFORE every CHG ± emollient application and 15 minutes POST application. Skin score, temperature and AEs will be monitored daily in all groups.

^dSkin to be assessed according to the skin score in Appendix I, once at screening. Skin score to be assessed BEFORE every CHG ± emollient application and 30 minutes POST application.

^e Nose swab to be taken BEFORE any CHG ± emollient application on day 1, day 3± 1 day and day 8 ± 3 days (closest working day) and at any time on this day in the control group. See Manual of Operations (MOP) for further details on how to take swabs.

^f A pooled swab of the cervical skin and umbilicus to be taken BEFORE any CHG \pm emollient application on day 1, day 3 ± 1 day and day 8 ± 3 days (closest working day) and at any time on this day in the control group. See MOP for further details on how to take swabs.

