5.2.1 CHLORHEXIDINE

Babies will be randomised to three different concentrations of chlorhexidine by dilution, 0.5%, 1% and 2%, to be applied daily (working days s only) or on alternate working days (three times a week) until day 14 after enrolment or discharge from hospital, whichever is earlier. Each baby will be allocated their own labelled bottle of the diluted product.

Before chlorhexidine is applied, the baby's temperature should be measured and the skin condition score assessment should be performed. Keeping the baby warm, treatment should be applied to the whole body (excluding face and eyes) using cotton wool, avoiding pooling of the chlorhexidine around the baby. After the application, the baby should be re-dressed and their body temperature should be measured after 15 minutes. The baby should be observed for skin reactions at 30 minutes after each application.

In the case of rare and highly unlikely accidents such as splash injury to the eye from chlorhexidine, flush the affected area with copious water or saline as quickly as possible, and consider whether referral for an opthalmological assessment is necessary.

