5.3 CONTROL GROUP

5.3.1 PRODUCTS

The control group will receive routine clinical care. Any skin product which is used will be recorded on CRFs/worksheets, along with the indication for its use.

The control group will receive assessments on alternate working days, including skin score, AE and temperature assessments, as well as swabs being taken on the protocol schedule.

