9.2 OUTCOME MEASURES

9.2.1 CO-PRIMARY OUTCOME MEASURES

- Skin bacterial load change in colony forming units (CFUs) in the nose (1 swab), cervical skin folds and umbilicus (1 pooled swab), and peri-rectal area (1 swab) from randomisation (before chlorhexidine application) to D3+/- 1 day and D8 +/- 3 days microbiology data collection (efficacy).
- Modified neonatal skin condition score (see Appendix I) used before each application of chlorhexidine, or alternate working days in controls (safety). The primary analysis of this outcome will consider the absolute score. Secondary analysis of this outcome will consider graded toxicity (see Appendix I).

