17 PROTOCOL AMENDMENTS

List of changes from v.1.0 (6th March 2020) to v.2.0 (29th November 2021):

- Trial registration (p6): Inclusion of ISRCTN number
- MRC CTU Staff (p8): Update to MRC CTU trial team (addition of [name])
- Trial Schema (p11), Summary of trial (p13), Section 9.2.2 Secondary outcome measures (p42): Addition of the acquisition & loss of *Pseudomonas aeruginosa* as a secondary outcome measure
- Trial Schema (p14), Section 3.3 Number of patients (p26): Removal of reference to recruitment targets of 91 babies per site
- Trial Assessment schedule (p15), Section 6.1 Trial assessment schedule (p34): Removal of collection of intrapartum antibiotic history as part of baseline data collection
- Section 3.1 Patient inclusion criteria (p26): Clarification that day 1 is defined as the second day of life, to align with section 1.4.1
- Section 5.3.1 Control group: Products (p32): Correction that control group receives assessment on alternate working days, not daily, which also aligns with section 6.1
- Section 7.3.3 Investigator assessment: Causality (p38): Correction of table numbers (from 3 to 2)
- Section 9.4 Interim monitoring & analyses (p43): Clarification that the DMC receives SAEs (not only SARs) on a weekly basis (not in real time)
- Section 13.2 Independent Data Monitoring Committee (DMC) (p49): Update to DMC committee members: removal of [name] as DMC chair; addition of [name] as DMC chair and of [name] as DMC member

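### The protocol sets two incompatible schedules for the co-primary skin score: every working day in all babies (6.3, Table 1 note c) and alternate working days in controls (5.3.1, 9.2.1)

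*Protocol*

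**What the plan says.** Two places require equal, frequent scoring. Section 6.3 states: "Skin score assessments will be performed once every working day on all babies to provide unbiased comparisons across randomised groups". Table 1 note c states: "Skin score, temperature and AEs will be monitored daily in all groups". The skin-score row of Table 1 fits this: it has a plain X on days 2, 4 and 8, where the application row has a bracketed X.

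Two other places differ. Section 5.3.1 states: "The control group will receive assessments on alternate working days, including skin score, AE and temperature assessments". Section 9.2.1, which defines the co-primary safety outcome, describes the skin score as "used before each application of chlorhexidine, or alternate working days in controls (safety".

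Table 1 note d adds: "Skin score to be assessed BEFORE every CHG ± emollient application and 30 minutes POST application". Section 6.1 covers the control schedule for other measurements: "Babies randomised to the control group will have swabs taken and temperature checked once on the same days" as the alternate-day arms. It does not mention the skin score for controls. Section 9.2.1 makes the absolute score the primary analysis of this outcome and graded toxicity a secondary one. Section 7.2 has non-serious adverse events documented at each scheduled visit, and section 9.5 compares them between groups.

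**The concern.** The skin score is the safety half of the pair of outcomes by which this pilot is to choose a regimen. Section 6.3 itself gives the reason for scoring everyone equally often. If sites follow 5.3.1 and 9.2.1 instead, the number of looks depends on control status and, on one reading, on the randomised application frequency.

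Any summary of the form at least one graded score, worst grade or any adverse event recorded at a visit rises with the number of looks, even when the true risk is the same in every arm. Allocation is open, and section 4.2 blinds only the laboratory staff, so equal scheduled ascertainment is one of the few protections this outcome has. Two sites could follow different sections and both be compliant. A later analysis plan can choose among scores that were taken, but it cannot recover control scores that were not.

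**Working it through.** The protocol states no figure for this point, so there is none to reproduce. The check compares the sections and then counts looks.

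**1. Do the statements conflict?**

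| Group | 6.3 and Table 1 note c | 5.3.1 and 9.2.1 | Compatible? |
|---|---|---|---|
| Controls | every working day | alternate working days | No |
| Alternate-day arms | every working day | before each application | Yes, unless 9.2.1 excludes scores on off-days |
| Daily arms | every working day | before each application | Yes |

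The hard conflict is therefore for controls: 182/13 = 14 babies. Note c also conflicts with 6.1 on control temperature (daily against the alternate-day schedule).

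**2. Scheduled scores, trial days 1 to 14.** Inputs: treatment to day 14 or discharge (5.2.1), and alternate working days fixed as Monday/Wednesday/Friday or Tuesday/Thursday/Saturday, that is, three a week.

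- Five-day week: 5 × 2 = 10 working days and 3 × 2 = 6 alternate days, whatever the starting weekday. If day 1 is not one of the fixed days, the day 1 assessment makes 7.
- Six-day week: 6 × 2 = 12 working days, against 6 (or 7).
- Discharge at day 7: 5 (or 6) against 3, before any added day 1 assessment.

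Under 6.3 and note c every arm has 10 (or 12). Under 5.3.1 and 9.2.1 the daily arms have 10 (or 12), and controls have 6 to 7. The alternate-day arms also have 6 to 7 if off-day scores do not count.

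**3. Effect on an any-event summary with no true difference.** The chance of at least one recorded event in k looks is 1 − (1 − p)^k, with the same p in all arms and independent looks. The value of p is an assumption; the protocol gives none.

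At p = 0.03:

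- k = 10: 1 − 0.97^10 = 0.263
- k = 7: 1 − 0.97^7 = 0.192
- k = 6: 1 − 0.97^6 = 0.167
- k = 12: 1 − 0.97^12 = 0.306

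The spurious ratios are 0.263/0.192 = 1.4 and 0.263/0.167 = 1.6 in a five-day week, and up to 0.306/0.167 = 1.8 in a six-day week.

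Range over p for 10 against 6 looks:

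| Assumed p per look | 10 looks | 6 looks | Ratio |
|---|---|---|---|
| 0.01 | 9.6% | 5.8% | 1.63 |
| 0.02 | 18.3% | 11.4% | 1.60 |
| 0.05 | 40.1% | 26.5% | 1.51 |
| 0.10 | 65.1% | 46.9% | 1.39 |

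**The case against.** **The primary analysis is largely protected.** Section 9.5 specifies a baseline-adjusted linear mixed model with individual as a random effect. Unequal numbers of planned visits do not by themselves bias a mean from such a model; they mainly change its precision. A reader might infer that the co-primary result itself is biased by the factor of 1.4 to 1.6. The documents do not support that: the factor applies to any-grade summaries, which are secondary for the skin score.

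**The alternate-day arms may be scored daily.** A reader might infer that babies are scored only on application days. The protocol does not say so. Scoring before each application can coexist with a daily score, and 6.3, note c and the Table 1 row all schedule off-day scores. This stands, and it is why the frequency comparison is affected only on a restrictive reading of 9.2.1.

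**The illustration is generous.** Dryness or erythema persists in a baby from day to day, so looks are correlated and the inflation shrinks. One could also count strict alternation, which the brackets in Table 1 might suggest, and reach 5 looks and a larger ratio. The protocol's stated definition is fixed weekdays three times a week, so 6 to 7 is the better count.

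**Adverse events are partly insulated.** These are inpatients, serious events are reportable whenever the investigator becomes aware of them, and many Appendix II grades rest on charted treatments. A per-look model fits those events poorly. The point carries over only to non-serious events that depend on the scheduled visit.

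**The move to alternate days was deliberate.** The amendment list records: "Correction that control group receives assessment on alternate working days, not daily, which also aligns with section 6.1". That indicates intent for 5.3.1, but 6.1 does not name the skin score, and 6.3 and note c still say otherwise. The conflict lies in the current text and does not rest on the list.

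**Conclusion.** The point holds as a contradiction in the schedule of a co-primary outcome: certain for the 14 controls, and dependent on the reading of 9.2.1 for daily against alternate-day arms. If 5.3.1 and 9.2.1 are followed, looks to day 14 are about 10 against 6 to 7 (12 against 6 to 7 in a six-day week).

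For the absolute score the consequence is mainly unequal precision and uncertainty about which scores enter the model. If scoring is tied to applications, babies whose treatment is permanently stopped may also contribute no further scores, and skin condition is one of the circumstances in which 5.2.1.2 has stopping considered. For any-grade or worst-grade skin toxicity, and for visit-recorded non-serious adverse events, arms with more looks would show more events without any true difference. At an assumed independent 3% per look the ratio is about 1.4 to 1.6 in a five-day week. The direction does not depend on that rate; the size does, and independence places it at the upper end.

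**What to change.** Reconcile 5.3.1, 6.3, 9.2.1 and Table 1 note c to a single skin-score and adverse event assessment schedule for all 13 arms, and reconcile 6.1 with note c on control temperature. In 9.2.1, define the co-primary safety outcome as one score per assessment day, taken before any application that day and recorded whether or not an application is given. This keeps the 30-minute scores, which only treated babies have, out of the between-arm comparison.

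If controls are to stay on alternate days, correct 6.3 and note c to say so. Then restrict the between-arm comparisons of skin score, worst grade and adverse events to assessment days common to all arms, and use the remaining scores descriptively.

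The first option costs wording changes and brief skin checks that 6.3 already requires: for controls, 10 − 7 = 3 to 10 − 6 = 4 extra days per baby in a five-day week (12 − 7 = 5 to 12 − 6 = 6 in a six-day week), plus off-day checks in the alternate-day arms if sites are not already doing them. The second costs no extra visits but leaves some daily-arm data out of the comparison. Neither removes the difference in time since the last application between daily and alternate-day arms; that is part of the frequency factor itself and should be borne in mind in interpretation.

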6.4 OTHER ASSESSMENTS

The baby's weight will be measured on the day of enrolment and the earliest of discharge or day 14.

6.5 EARLY STOPPING OF FOLLOW-UP

If a parent/carer (who gave consent) chooses to discontinue their baby's trial treatment, the baby should always be followed up providing the parents/carers are willing; that is, they should be encouraged to not leave the whole trial. If the parents/carers do not wish their baby to remain on trial follow-up, however, their decision must be respected and the baby will be withdrawn from the trial completely. The MRC CTU should be informed of this in writing via email and early stopping detailed in the clinical notes.

The medical data collected during the baby's participation in the trial will be kept for research and analysis purposes, in a pseudonymised format (identified only by their trial number). Consent for future use of stored samples already collected can be refused when leaving the trial early (but this should be discouraged and should follow a discussion).

Parents may change their minds about stopping trial follow-up at any time and re-consent to participation in the trial.

6.6 PATIENT TRANSFERS

If a baby moves from the trial hospital to another hospital during the trial, further application and assessments related to the trial will not be continued at the other hospital. The 28 day follow-up phone call will still be done to ascertain vital status and will be documented in a telephone follow-up sheet provided by the MRC CTU and filed in the baby's trial file.

6.7 FOLLOW-UP

Follow up will be until 28 days after randomisation, which will be via phone call if the baby has already been discharged. At day 28 the baby's vital status will be ascertained, together with occurrence of serious adverse events (including clinically defined sepsis, necrotising enterocolitis (NEC)) and any unscheduled visits to healthcare providers. Parents/carers will be provided with the trial team's details at discharge and will be told to bring their baby back to the hospital if they have any concerns.

6.8 COMPLETION OF PROTOCOL FOLLOW UP

Each baby will complete follow-up in the trial at their day 28 visit.

7 SAFETY REPORTING

The principles of GCP require that both investigators and Sponsors follow specific procedures when notifying and reporting adverse events or reactions in clinical trials. These procedures are described in this section of the protocol. **Section 7.1** lists definitions, **Section 7.2** gives details of the investigator responsibilities and **Section 7.4** provides information on the MRC CTU responsibilities.

